23.5 Monitoring

Monitoring Personnel: See Help Bubble to the right.

Internal Monitoring

The PI or his/her designee shall conduct internal monitoring to assure the safe and proper conduct of the protocol and all the elements list above in monitoring, following the general principles of quality management. The intensity and frequency of internal monitoring will depend on the protocol risk to participants, the experience of the PI and research team, rate of enrollment, and specific details of the protocol.

Internal monitoring of informed consent and eligibility documentation will be conducted by the research team shortly after enrollment begins. Internal monitoring activities will be documented by logs, meeting minutes or other systematic means.

Specify the research team members who will conduct the internal monitoring of the study (see Help for who may monitor):

Internal monitoring will be performed by [name]

For new investigators: Internal monitoring should be conducted at least monthly by new investigators until there are essentially no findings to correct at each review.

External Monitoring

* Is external monitoring planned for this protocol?

- Yes
 No
 Unsure

If external monitoring is planned, please specify (see Help for who may monitor):

- (Significant Risk) External monitoring will occur at least every six weeks unless there is no enrollment
 (Moderate Risk) External monitoring will occur at least quarterly
 (Low or Minimal Risk) External monitoring will occur at least annually

If external monitoring is planned, please specify the name of the monitor:

- Note that copies of external monitoring reports must be supplied to the IRB and the CRSO as soon as they are made available

Additionally, audits of the research records of minimal, moderate or significant-risk protocols may be performed by the CRSO staff on a random basis or as part of a prospectively identified auditing plan.

23.6 Adverse Event Classification

Adverse events are classified by definition, severity, and association with the investigational trial.

Definition of an Adverse Event

Any unfavorable or unintended sign (including abnormal lab findings), symptom or disease temporally associated with the use of a medical treatment or procedure, or protocol, regardless of whether it is considered related to the medical treatment or procedure or protocol.

Definition of a Serious Adverse Event

Any unanticipated event that involves the following:

- o results in death
- o is life-threatening
- o requires hospitalization or prolongs existing hospitalization
- o results in persistent or significant disability/incapacity
- o is any medical event which requires treatment to prevent one of the outcomes listed above

Other events can be classified as "serious adverse events" at the discretion of the PI.

Definition of Anticipated/Expected Adverse Event

Any adverse event, which has been reported in the Investigator's Brochure, package insert, safety reports, clinical protocol, consent form or listed in the NCI agent-specific Expected Adverse Event List³, is classified as an expected adverse event.

The investigator must provide the available data of known adverse events and toxicities that have been associated with the study drug, device, intervention, or procedures. This information helps to define the level of risk of the trial and enables safety monitoring. A minimal risk trial may not have any defined risks and a statement to that effect is sufficient to meet the DSMP requirements.

Definition of an Unanticipated/Unexpected Adverse Event

Any adverse event that is not consistent with the known, predicted possible effects of the research protocol. An unexpected adverse event varies in nature, intensity or frequency from information on the investigational product provided in the Investigator's Brochure, package insert, safety reports, clinical protocol, or listed in the consent form.

Definition of an Unanticipated Problem (UaP)

A UaP is an event or circumstance that meets all the following three criteria: [1] the nature, severity, frequency of the event (s) or information was not expected in the descriptions in the study documents or the characteristics of the participant population being studied; [2] there is a reasonable possibility that the procedures involved in the research caused or are linked in a significant way to the problem; [3] the event or information suggests that the research places participants or others at a greater risk of harm than was previously known or recognized (including physical, psychological, economic, or social harm).

Grade and Relatedness of Adverse Events:

Adverse Events are graded for severity and scored for relatedness to the protocol, according to a published scale. Several standardized AE Reporting scales are available. (See Help for links to these scales.)

* Please indicate the scale you intend to use:

- CTC v2.0 (<http://ctep.info.nih.gov/reporting/ctc.html>)
- CTCAE v3.0 (http://ctep.info.nih.gov/protocolDevelopment/electronic_applications/docs/ctcae3.pdf)
- CTCAE v4.0 (http://evs.nci.nih.gov/ftp1/CTCAE/CTCAE_4.03_2010-06-14_QuickReference_8.5x11.pdf)
- CTCAE v5.0 (https://ctep.cancer.gov/protocoldevelopment/electronic_applications/docs/CTCAE_v5_Quick_Reference_8.5x11.pdf)
- AIDS Clinical Trials Group (<http://aactg.s-3.com/>)
- Other

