20.0 Potential Risks to Participants

20.1 * Describe any potential risks: physical, psychological, social, legal or other and assess their likelihood and seriousness. Indicate risks both to the participants and to the embryo or fetus if the participant is or may become pregnant. Please provide the potential risks below:

Potential side effects associated with study drug (Secukinumab) includes but is not limited to infection, inflammatory bowel disease, and allergic reactions.

Infections

Because Secukinumab suppresses the immune system, it may increase the risk of infections. In clinical trials with patients who had moderate to severe psoriasis, a higher rate of infections was observed in Secukinumab treated subjects compared to placebo-treated subjects. A higher rate of common infections, such as nose and throat (11.4% vs 8.6%), upper respiratory infection (2.5% vs 0.7%) and skin and mucous membrane candida (1.2% vs 0.3%) were observed with Secukinumab compared with placebo. A similar increase in risk of infection was seen in placebo-controlled trials in patients with psoriatic arthritis and ankylosing spondylitis.

Inflammatory Bowel Disease

In clinical trials of patients with plaque psoriasis, psoriatic arthritis and ankylosing spondylitis, there has been worsening of known inflammatory bowel disease, in some cases serious. In addition, new onset inflammatory bowel disease cases occurred in clinical trials with Secukinumab. In an exploratory study in 59 patients with active Crohn's disease, there were trends toward greater disease activity and increased adverse events in the Secukinumab group as compared to the placebo group. Patients who are treated with Secukinumab should be monitored for signs and symptoms of inflammatory bowel disease.

Allergic Reactions

Sometimes people have allergic reactions to drugs. Anaphylaxis and cases of hives occurred in Secukinumab treated patients in clinical trials. Some things that happen during an allergic reaction that could be a sign or symptom of a life-threatening allergic reaction are:

- A rash
- Difficulty breathing
- Wheezing
- A sudden drop in blood pressure

- Swelling around the mouth, throat or eyes
- A fast pulse
- Sweating

Cancer

Drugs similar to Secukinumab have been known on rare occasions to be associated with certain cancers. This has not been observed with Secukinumab.

Risks Related to Skin Biopsy

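### The SAE definition in section 23.6 requires an event to be unanticipated, so a serious event already listed as a known risk is an SAE only if the PI chooses

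*Combined protocol and SAP*

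**What the plan says.** Section 23.6 opens its definition of a serious adverse event with "Any unanticipated event that involves the following". Five outcomes follow: death, threat to life, hospitalisation, disability, and an event needing treatment to prevent one of these. All five sit under that opening condition. For everything else the section offers one permissive sentence: "Other events can be classified as 'serious adverse events' at the discretion of the PI".

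The section then defines expectedness. An event already reported in the Investigator's Brochure, package insert, safety reports, protocol or consent form "is classified as an expected adverse event". The counterpart reads: "An unexpected adverse event varies in nature, intensity or frequency from information on the investigational product".

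Section 20.1 lists the known risks. On allergy it says "Anaphylaxis and cases of hives occurred in Secukinumab treated patients in clinical trials", and it gives signs that "could be a sign or symptom of a life-threatening allergic reaction". On the bowel it says "new onset inflammatory bowel disease cases occurred in clinical trials with Secukinumab".

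Section 23.7 sets the reporting times. SAEs go to the IRB within two working days, according to policy. Unanticipated AEs that are related and more than moderate in severity have the same limit. All AEs are reported no less than once a year.

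Secondary outcome 6 in section 12.8 is the frequency and severity of AEs and SAEs over the whole trial, and aim 5 in section 12.6 compares safety between the arms over the first three months.

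**The concern.** Seriousness and expectedness answer different questions. Seriousness describes the outcome of an event. Expectedness describes whether the event was already known. Section 23.6 makes the second a precondition of the first, so an event with a serious outcome can fall outside the SAE definition because the drug is already known to cause it.

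Three things depend on the SAE label: the two-working-day IRB report, the SAE part of secondary outcome 6, and consistent counting from patient to patient. For a listed serious event, each depends on what the PI decides in that case.

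The effect may also be uneven between arms. Until week 12 only Group 1 receives secukinumab, and the listed drug risks are secukinumab risks. If such events occur more often on drug, those without automatic SAE status would fall mainly in Group 1 during the placebo-controlled period.

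**Working it through.** The plan states no figure to reproduce. The check is to apply the definitions in 23.6 to the risks in 20.1 and follow each event through the reporting rules in 23.7.

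**Step 1: is the event expected, and is it then an SAE?**

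| Event | What section 20.1 discloses | Status under 23.6 as written |
|---|---|---|
| Life-threatening anaphylaxis | Anaphylaxis reported on secukinumab; signs of a life-threatening reaction described | Expected in kind and in intensity; an SAE only at PI discretion |
| New-onset inflammatory bowel disease, serious case | Reported, no severity stated | Arguable: listed, but a serious case may exceed the disclosed intensity |
| Worsening of known inflammatory bowel disease | Reported, serious in some cases | Expected, but a history of the disease is excluded (13.12, item 3) |
| Hospitalised infection | Rates given for common infections only | Ambiguous: may differ in intensity and so count as unexpected |

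The last outcome in the SAE list refers to any medical event, but it sits under the same opening condition and so does not remove it.

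**Step 2: does another route catch an expected serious event?**

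- The unanticipated-AE route in 23.7 applies only to events that are not expected.
- An unanticipated problem must meet three criteria together. The first is that the nature, severity or frequency "was not expected in the descriptions in the study documents". An expected event fails it.
- Section 24.1 has grade 3 or greater AEs judged for relatedness as a withdrawal criterion. That gives neither an SAE label nor an IRB report.
- What remains is the general rule in 23.7 that AEs reach the IRB no less than once a year.

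So, for life-threatening anaphylaxis that the PI does not elect to call serious, the protocol's stated IRB interval moves from two working days to the yearly minimum.

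**Step 3: what does one label do to the reported rate?**

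Input: n = 20 per arm (section 14.2). The single event is illustrative; the documents give no expected rate. Exact (Clopper-Pearson) 95% limits:

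- 0/20: rate 0%. Upper limit = 1 − 0.025^(1/20) = 0.168, so 0 to 16.8%.
- 1/20: rate 5.0%. Lower limit = 1 − 0.975^(1/20) = 0.001. The upper limit is the value of p that solves (1 − p)^20 + 20p(1 − p)^19 = 0.025, which is 0.249. The interval is 0.1% to 24.9%.

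**The case against.** The best counter-argument attacks the leading example. Section 20.1 says that anaphylaxis occurred, without grade or frequency; the life-threatening wording is in a separate, general sentence about warning signs. On a strict reading, a life-threatening case might still differ in intensity and so be unexpected. This does not succeed. The protocol lists anaphylaxis by name and describes the allergic reaction as potentially life-threatening in the same paragraph, so both kind and intensity are disclosed. That a careful reader could argue the point either way is itself a reason not to let SAE status turn on it.

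Several other points stand, and they limit the size of the problem:

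- The institutional policy cited in 23.7 is not in the documents and may require faster reporting. The yearly interval is a minimum, not a delay that the protocol imposes.
- The event is not lost. It remains in the AE data with a severity grade, and 21.1 and 24.1 provide clinical safeguards that do not depend on the SAE label.
- Section 12.10 describes no formal test on SAEs, and the 0/20 and 1/20 intervals overlap heavily, so no inference is shown to change.
- The trial is double-blind, so PI discretion need not differ by arm. Blinding limits bias in the choice but does not turn the choice into a rule.
- Parts of 23.6 and 23.7 read like an institutional form, so the study team may not control the wording. This is an inference from style.

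**Conclusion.** The concern holds. As written, section 23.6 can deny a listed serious event its SAE label and its two-working-day IRB report, and no other provision in the documents restores them. Life-threatening anaphylaxis is the clear case, serious new-onset inflammatory bowel disease is arguable, and hospitalised infection is ambiguous.

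The consequence is limited to labelling, the timing of IRB notice and consistent counting in secondary outcome 6. One relabelled event shifts an arm's SAE rate by five percentage points (1/20).

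The conclusion rests on two conditions: that the policy behind 23.7 does not override the protocol's definition, which cannot be checked here, and that the definition is applied literally. Nothing in the documents shows that such an event has occurred or been mislabelled. The wording should be corrected, but this does not threaten the primary analysis.

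**What to change.** Delete *unanticipated* from the SAE definition so that any adverse event with one of the listed outcomes is serious. Keep expectedness as a separate attribute that decides only whether the unanticipated-event route also applies. If the form wording is fixed by the institution, add a protocol-specific note to the same effect.

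State in section 12.10 that SAEs are tabulated by arm regardless of expectedness.

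Recruitment is closed (section 17.1), so also re-check the existing AE log before analysis, preferably without knowledge of allocation, and reclassify any event that meets a listed outcome.

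The cost is one word or a short note, one sentence in the analysis section, a review of the log for 40 patients, and possibly a few additional SAE reports. No treatment or clinical rule changes.

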23.7 Reporting Adverse Events

All AEs will be reported to the IRB at least annually.

Reporting Serious AEs

- Serious Adverse Events, (SAEs) will be reported to the IRB according to policy, within two working days of identification of the SAE.

Select all that apply:

- SAEs will be reported to the Sponsor and or ESCROW

SAEs will be reported to the sponsor within how many days of the event?

- SAEs will be reported directly to the FDA, per 21 CFR 312

SAEs must be reported directly to the FDA within 7 days of the event by the investigator/sponsor.

- SAEs will be reported to another entity

Describe:

Reporting Unanticipated AEs:

Select all that apply:

- UAEs will be reported to the IRB

UAEs that are related and greater than moderate severity must be reported to the IRB according to policy, within two working days of identification of the UAE.

- UAEs will be reported to the Sponsor

UAE will be reported to the sponsor within how many days of the event?

UAEs will be reported to the FDA, per 21 CFR 312

UAEs will be reported to the FDA, per 21 CFR 312, within 15 days.

UAEs will be reported to another entity

Describe:

23.8 Reporting Unanticipated Problems

Unanticipated problems involving risks to participants or others will be reported to the IRB and the CRSO within five working days.

23.9 CLIA/CLEP

Only laboratory and research tests that are CLIA/CLEP certified or waived may be used to determine eligibility, shared with research volunteers, and used in clinical decision making.

Select if applicable:

This study includes tests that are not CLIA/CLEP certified; the results of such tests will not be used in clinical decision making, or to determine eligibility, or shared with participants or their health care providers.

23.10 Tissue Repository

Human Tissue and Data Repositories collect, store, and distribute human tissue materials and or data for research purposes. Repository activities involve three components: (i) the collectors of tissue samples\data; (ii) the repository storage and data management center; and (iii) the recipient investigators.

* Select one:

- I DO NOT intend to collect, store, and distribute human tissue materials for research purposes
- I DO intend to collect, store, and distribute human tissue materials for research purposes, therefore this protocol entails the Operation of a Tissue Repository. The IRB requires that the protocol specify the conditions under which data and specimens may be accepted and shared, and ensuring adequate provisions to protect the privacy of participants and maintain the confidentiality of data.

If you do intend to collect, store, and distribute human tissue materials, you will be asked to upload the following documents later on in the submission:

- A Sample collection protocol (for tissue collector collaborators to follow) and informed consent document for distribution to tissue collectors and their local IRBs.
- A Certificate of Confidentiality (to protect confidentiality of repository specimens and data).
- A Recipients Agreement describing the commitment of the recipient to preserve the anonymity of the samples shared.

24.0

Toxicity Management and Stopping Rules

24.1 * Describe any drug toxicity or other conditions under which the participation of a participant or the conduct of the study would be stopped in order to maximize safety (e.g., toxicity management and stopping rules):

Suspend Secukinumab or study drug placebo administration if the participant develops an infection or other AE that the investigator judges to be significant. If the infection or AE resolves, Secukinumab or study drug placebo may be restarted at the next scheduled dose.

* Indicate withdrawal criteria and procedures below:

- 1) A grade 3 or greater AE that the protocol chair and/or the medical monitor, in consultation with the site investigator, judge to be possibly, probably, or definitely related to Secukinumab.
- 2) Two sequential doses of Secukinumab are withheld.

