13.12 Exclusion Criteria

Please list participant exclusion criteria:

Order Number	Criteria
1	Has a nonplaque form of psoriasis (eg, erythrodermic, guttate, or pustular)
2	Has previously received Secukinumab or other biologics
3	History of Inflammatory Bowel Disease (IBD)
4	History of Rheumatoid Arthritis
5	Use of topical treatments for psoriasis, including steroids, vitamin D derivatives, vitamin A derivatives, salicylic acid, tar (except moisturizers) and/or UVA/UVB phototherapy within the last 2 weeks (if these have used them, the participant needs to wash off of them for at least 2 weeks after signing consent prior to baseline)
6	Is pregnant, nursing, or planning a pregnancy (both men and women) within 5 months following the last administration of study drug
7	Has recently received or is planning to receive a vaccination while on the study
8	HIV positive
9	Chronic untreated hepatitis C, positive hepatitis B surface antigen
10	Known tuberculosis (TB) or evidence of TB infection. Subjects with a positive QuantiFERON® TB test or a positive purified protein derivate (PPD) skin test result may participate in the study if further work up (according to local practice /guidelines) establishes conclusively that the subject has no evidence of active TB.
11	Any severe, progressive or uncontrolled medical condition at screening that in the judgment of the investigator prevents the subject from participating in the study.

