21.0 Procedures to Minimize Risks

21.1 * Describe the procedures for protecting against or minimizing any potential risks, and include an assessment of their likely effectiveness. Include a discussion of confidentiality safeguards, where relevant, and arrangements for providing medical treatment, if needed.

The increased risks of infections are minimized by screening for latent tuberculosis infection. The risks of infection are also minimized by reporting any infections to the Study Team or the Study Staff, as well as any fever, chills, loss of appetite, throat pain, cough or colds. In some cases of infection, the Study Team may decide that the study drug should be discontinued.

The risks of exacerbating autoimmune disorders is minimized by screening for and excluding individuals with known inflammatory bowel diseases. Any change in bowel habits, including diarrhea, cramps, and blood in the stool, will be reported to the Study Team during the study.

If an allergic reaction occurs, administration of Secukinumab will be discontinued immediately and appropriate medical therapy will be given. Subject will be asked to remain at the Study Site for two hours following administration of the Study injections. Subject will be observed during this time for any sensitivity reactions. Subject should get medical help and contact the Study Team if subject have any of these or any other side effects during the study.

Women who are pregnant or nursing must not participate in this trial. The risks of teratogenicity are minimized by screening for pregnancy at each visit. If subject is a woman who is able to become pregnant, subject should use an effective form of birth control (contraception) during the study and for 20 weeks after the last dose of study drug. Subject may choose to use an occlusive cap (diaphragm or cervical/vault cap) with spermicide or subject's male partner can use a condom combined with a spermicidal foam/gel/film/cream/vaginal suppository. The following methods are more effective and are also acceptable: 1) total abstinence from male/female intercourse, or 2) male/female sterilization or 3) use of oral, injected or implanted hormonal methods of contraception (in case of oral contraception subject should have been using the same pill on a stable dose for a minimum of 3 months before taking study drug), or 4) placement of an intrauterine device (IUD) or intrauterine system (IUS). If subject

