becomes pregnant or suspect being pregnant during the study, subject must inform the Study Team immediately. Subject will not be allowed to continue study drug if subject is pregnant. Study Team will medically follow subject's pregnancy and collect information about the pregnancy until delivery to monitor the subject and subject's child's safety.

Skin biopsies will be performed using sterile technique. Treatment of the area post-procedure will include the use of an antibiotic ointment and the application of dry, sterile dressing. The subject will be taught how to care for the biopsy site and will be given the supplies to do so. All procedures will be performed by trained qualified staff.

Samples of skin are to be identified by number and not by patient name in an effort to protect confidentiality. A confidential master codebook will be kept by the PI. The study coordinator, or investigator, manages protocol-specific data on paper forms organized by patient number and/or study. These are kept in a secure, double-locked area of the lab. All lab personnel that work with patient data or samples have passed human subject protection courses and will keep data confidential in designated laboratory files. Data are not recorded in computerized spreadsheets, except for final analysis of data. Since Microsoft Excel is often used for data analysis, only the primary "sheet" is used and data cannot be copied to another sheet. Data entries are certified against primary source documents in the lab.

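### Sections 21.1 and 24.1 do not agree on whether study injections may resume after a resolved allergic reaction below grade 3

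*Combined protocol and SAP*

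**What the plan says.** Section 24.1 (Toxicity Management and Stopping Rules) works in three steps.

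- Suspension: "Suspend Secukinumab or study drug placebo administration if the participant develops an infection or other AE that the investigator judges to be significant".
- Restart: "If the infection or AE resolves, Secukinumab or study drug placebo may be restarted at the next scheduled dose".
- Withdrawal, on either of two criteria. The first reads in part "A grade 3 or greater AE that the protocol chair and/or the medical monitor, in consultation with the site investigator, judge to be possibly"; any stronger link to the drug counts as well. The second is "Two sequential doses of Secukinumab are withheld", with no condition on grade or relatedness.

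It names neither allergic reaction nor pregnancy.

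Section 21.1 (Procedures to Minimize Risks) sets its own treatment consequences. For allergy: "If an allergic reaction occurs, administration of Secukinumab will be discontinued immediately and appropriate medical therapy will be given". For pregnancy: "Subject will not be allowed to continue study drug if subject is pregnant". For infection it leaves discontinuation to the study team's judgment.

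Section 20.1 lists allergic reactions among the main side effects of the drug. It reports that anaphylaxis and hives occurred in earlier trials, without giving a frequency.

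**The concern.** Section 24.1 is where an investigator looks to decide whether injections stop or resume. The form's own prompt there asks for the conditions under which a participant would be stopped. Section 21.1 contains such a condition for allergic reaction, and 24.1 does not repeat it, refer to it or exempt it from the restart sentence.

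A participant with a mild allergic reaction that clears the same day could be taken off injections or given the next one, depending on which section is consulted. What is at stake is re-exposure after an allergic reaction, a hazard the protocol itself foresees. Consistent handling matters too, because the decision also determines who is still on treatment at week 12 and week 24.

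**Working it through.** There is no plan figure to reproduce. The check sets the two sections side by side and then reads the timing from the visit table in section 12.9.

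**1. Does 24.1 cover allergic reactions?** Section 23.6 defines an adverse event broadly enough to include one. If the investigator judges it significant, the 24.1 suspend and restart steps apply. If not, 24.1 calls for no action at all.

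**2. Case by case**

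| Event | Section 21.1 | Section 24.1 | Result |
|---|---|---|---|
| Allergic reaction below grade 3, resolved | Discontinue at once | Restart permitted; criterion 1 not met | Unreconciled |
| Allergic reaction, grade 3 or above, at least possibly related | Discontinue at once | Withdraw (criterion 1) | Consistent |
| Pregnancy | Study drug may not continue | Silent | Omission from 24.1 |
| Infection | Study team may discontinue | Suspend if significant; restart permitted | Compatible |

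**3. Is discontinuation in 21.1 final?** The section does not say. Two points suggest that it may be: 24.1 uses a different verb, suspend, for a temporary stop, and section 12.9 uses discontinue for the end of treatment after week 24. Neither amounts to a definition.

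**4. Timing.** The visit table schedules injections at baseline and weeks 1, 2, 3, 4, 8, 12, 13, 14, 15, 16, 20 and 24. That is 13 injections and 13 − 1 = 12 intervals.

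- 7-day intervals: 0–1, 1–2, 2–3, 3–4, 12–13, 13–14, 14–15 and 15–16, which makes 8.
- 28-day intervals: 4–8, 8–12, 16–20 and 20–24, which makes 4.

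These are nominal, before visit windows. Group 2 receives placebo before week 12, and Group 1 receives placebo at weeks 13 to 15. So each group has four 7-day intervals between two active doses: Group 1 in the first weekly run, Group 2 in the second. Blinded staff cannot tell which applies.

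**5. Does the two-withheld-doses criterion close the gap?** Not by itself.

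- If the reaction resolves before the next injection and dosing resumes, withheld doses = 0, below the 2 required.
- If injections stop for good under 21.1, the criterion is met once two have been missed, provided two remain. After an event at week 16, two remain (weeks 20 and 24). After week 20 only one remains, and after week 24 none, so the criterion cannot then be reached.

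**6. Wording under the blind.** The suspend and restart sentences name drug or placebo. The 21.1 allergy sentence and the second withdrawal criterion name only Secukinumab. Read literally, blinded staff cannot know whether either applies to the injection just given or withheld.

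**The case against.** The strongest reply is that the sections can be followed together. Restart in 24.1 is permissive and never requires re-dosing. An investigator who stops for an allergic reaction and does not restart complies with both. Section 21.1 can be read as the specific rule and 24.1 as the general one, and a lasting stop under 21.1 would often lead to withdrawal through the second 24.1 criterion.

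This stands to the extent that a reader who inferred two opposite rules would be going too far. It does not remove the overlap. Nothing in the text says that 21.1 governs, and 24.1 on its own allows re-dosing after an event for which 21.1 calls for discontinuation.

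Other stronger inferences also lack support:

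- **Pregnancy as a second conflict.** Section 24.1 is silent, and silence does not contradict the explicit bar in 21.1. It is only missing from the list.
- **New inflammatory bowel disease as a third conflict.** A history of the disease excludes entry (section 13.12), and 21.1 requires bowel changes to be reported, but no section sets an on-treatment stopping rule for 24.1 to contradict. An entry criterion is not such a rule.
- **Withdrawal for grade 3 or higher related events alone.** This overlooks the second criterion.
- **Different practice across sites.** Section 12.9 describes a single-center trial.

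**Conclusion.** The point holds as an internal inconsistency between 21.1 and 24.1, confined to allergic reactions below grade 3 that resolve. Within that range the protocol does not tell the investigator whether injections may resume, and the next one is nominally 7 days away at 8 of 12 intervals. The absence of the pregnancy rule from 24.1 is a lesser omission that the same edit can close.

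The documents give no allergic-reaction rate, so neither the expected number of participants nor any effect on week 12 or week 24 results can be estimated. The sample size and power figures do not depend on this point.

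The conclusion assumes that an allergic reaction counts as an adverse event under section 23.6 and that the visit table is the operative schedule. It takes no view on which rule is clinically right.

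**What to change.** Reconcile sections 21.1 and 24.1 in one edit:

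- State a single rule for allergic reaction in 24.1, including whether discontinuation in 21.1 is final or a suspension.
- Make the restart sentence consistent with that rule.
- Carry the existing 21.1 pregnancy rule into 24.1 by cross-reference.
- Word the rules, including the second withdrawal criterion, in terms of study injections (drug or placebo) so that they can be applied under the blind.

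The sponsor and investigator decide which rule stands. The cost is a wording amendment, with no added visits, tests or participants. Section 17.1 says recruitment is closed. If dosing has also finished, the useful step is to record which rule was applied to any allergic reaction that occurred.
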